5.18. Other Analyses

5.18.1. Columbia-Suicide Severity Rating Scale (C-SSRS)

The baseline and maximum post-baseline results from the C-SSRS will be summarized. The maximum of each subscale (suicidal ideation [Categories 1-5], suicidal behavior [Categories 6-10], suicidal ideation or behavior [Categories 1-10], and self-injurious behavior without suicidal intent) will be presented. The number of patients with suicide-related treatment-emergent events, treatment-emergent suicidal ideation, and suicidal behavior, based on a comparison of the C-SSRS at baseline and/or previous lifetime experience to maximum C-SSRS scores across all post-baseline assessments will be provided. All C-SSRS elements will be reflected in a listing.

5.18.2. HAM-A Scores

The HAM-A domain scores and total score will be listed by treatment group and study visit. The total score will be summarized by treatment group.

5.18.3. Penn Physician Withdrawal Checklist

The PWC individual items and total score will be listed by treatment group and study visit. The total score will be summarized by treatment group.

5.18.4. EQ-5D-5L

The EQ-5D-5L individual scores of the 5 dimensions, the total index score, health state and VAS score will be listed by treatment group and study visit. The total index score and VAS score and changes from baseline will be summarized by treatment group.

5.18.5. Sheehan's Disability Scale

The SDS scores will be listed by treatment group and study visit. The SDS score and change from baseline will be summarized by treatment group.

5.19. Pharmacokinetics

All PK listings and individual plasma concentration-time profiles will be presented using the Safety Analysis Set. PK summary tables, mean figures and all statistical analyses will be presented using the PK Analysis Set.

5.19.1. Pharmacokinetic Sampling

With participants maintaining their normal BID dosing routine, a single daytime blood sample for determination of plasma darigabat concentration will be collected at Visits 3, 4, 5, and 6. The date and time of the PK sample, as well as the time of ingestion of previous dose of IMP, will be recorded in the source documentation.

5.19.2. Pharmacokinetic Data Handling

Concentration values that are below the level of quantification (BLQ) will be set to zero for summary tables. Individual values that are BLQ will be presented as "BLQ" in the concentration data listing.

5.19.3. Pharmacokinetic Analysis

Darigabat plasma concentrations will be summarized by dose and day, where applicable, using descriptive statistics including the arithmetic mean, median, standard deviation, coefficient of variation, minimum and maximum values, and geometric mean.

Plasma concentrations will also be pooled with data from other trials in a population PK analysis to describe the time course of plasma concentrations of darigabat and the influence of covariates (e.g., body weight, age, sex, race, concomitant medications) on PK parameters. Plasma concentration may also be pooled with data from other trials in a physiologically based PK model. The results of these analyses are outside the scope of this SAP.

5.20. Protocol Deviations

All protocol deviations will be reviewed by the project team prior to unblinding to identify participants with important protocol deviations. Summaries of important deviations will be presented by category and subcategory of deviation for the FAS: Expanded Analysis Set. All deviations from the protocol will be listed by category along with a description and any additional comments.

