**Table 7: Analysis Set Descriptions**

Term	Description	Analysis
ITT	All randomized participants.	Demographic and Baseline Characteristics
Safety Analysis Set	All randomized participants, who receive at least 1 dose of IMP. This will be the safety analysis set.	Safety analysis
FAS	Panic Attack Endpoints All randomized participants who receive at least 1 dose of IMP and have valid baseline panic attack assessments and have recorded all baseline/post-baseline panic attack assessments in an eDiary that requires collection of reports contemporaneous to the day being assessed and collection of the presence/absence of each associated symptom. Participants who have not met all inclusion/exclusion criteria but are randomized in error will not be included.	All efficacy analysis (including primary) related to panic attack events captured by eDiary
	Non-Panic Attack Endpoints All randomized participants who receive at least 1 dose of IMP and have valid baseline panic attack assessments. Participants who have not met all inclusion/exclusion criteria but are randomized in error will not be included.	All other efficacy analysis
PK Analysis Set	All randomized participants who receive at least 1 dose of IMP and have at least 1 measurable darigabat concentration.	PK analysis

Abbreviations: FAS=full analysis set; IMP=investigational medicinal product; ITT=intent-to-treat; PK=pharmacokinetic.

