5.2. Analysis Sets

The analysis sets are defined as follows:

Table 14: Analysis Set Descriptions

Term	Description	Analysis
All Screened Participants	All Screened Participants includes all participants who signed the informed consent form.	Disposition
Intent-to-Treat Analysis Set (ITT)	All randomized participants.	Demographic and Baseline Characteristics
Safety Analysis Set	All randomized participants who receive at least 1 dose of IMP.	Safety analysis
Full Analysis Set (FAS)	
FAS: Panic Attack Endpoints
 
All randomized participants who receive at least 1 dose of IMP and have valid baseline panic attack assessments and have recorded all baseline/post-baseline panic attack assessments in an eDiary that requires collection of reports contemporaneous to the day being assessed and collection of the presence/absence of each associated symptom (i.e. eDiary Version 2). Participants who have not met all inclusion/exclusion criteria but are randomized in error will not be included.
	All efficacy analysis (including primary) related to panic attack events captured by eDiary

Term	Description	Analysis
	FAS: Expanded All randomized participants who receive at least 1 dose of IMP and have valid baseline panic attack assessments. Participants who have not met all inclusion/exclusion criteria but are randomized in error will not be included.	Sensitivity efficacy analysis (including primary) related to panic attack events as specified
PK Analysis Set	All randomized participants who receive at least 1 dose of IMP and have at least 1 measurable darigabat concentration.	PK analysis

Abbreviations: FAS=full analysis set; IMP=investigational medicinal product; ITT=intent-to-treat; PK=pharmacokinetic.

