5.8. Exposure to Treatment

The number of participants who received IMP, number of days on IMP, number of treatment discontinuations, reasons for treatment discontinuation, and treatment compliance will be summarized by treatment group for the FAS: Expanded Analysis Set. Drug accountability data will be listed.

5.9. eDiary Compliance

Primary, secondary, and other efficacy variables are based on diary-collected panic attack frequencies, and as such, diary compliance will be evaluated along with treatment compliance. Participants are instructed to complete their diary entries at least once a day during the study. A diary day will be considered missing for compliance if a panic attack diary record is missing for that day. Diary compliance will be evaluated during the Screening Period, the Baseline Period, the Titration Period, the Maintenance Period, the entire Treatment Period, and the last two weeks of Maintenance Treatment.

eDiary compliance will be calculated as 100 times the number diary days (days with diary completed) during the period and dividing this quantity by the expected number of diary days that should have been completed during this period of time. Compliance is computed for actual time of participation in the study through Visit 8 follow-up. If a participant did not enter an analysis period, the diary compliance for the analysis period will not be calculated.

eDiary compliance data will be listed by treatment then participant for each diary type and summarized by treatment group and version of diary used.

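### The important-deviation and exposure summaries are run on FAS: Expanded, which excludes ineligible participants randomised in error; ITT and the Safety Analysis Set fit better, and Table 14 should name a set for the non-diary endpoints

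*SAP*

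**What the plan says.** SAP 5.20 (Protocol Deviations): "Summaries of important deviations will be presented by category and subcategory of deviation for the FAS: Expanded Analysis Set". The same section says that every deviation will also be listed.

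SAP 5.8 (Exposure to Treatment) covers the number who received IMP, days on IMP and treatment discontinuations, and ends: "reasons for treatment discontinuation, and treatment compliance will be summarized by treatment group for the FAS: Expanded Analysis Set".

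SAP Table 14 (section 5.2) defines FAS: Expanded in two sentences: "All randomized participants who receive at least 1 dose of IMP and have valid baseline panic attack assessments" and "Participants who have not met all inclusion/exclusion criteria but are randomized in error will not be included". The use it gives for the set is "Sensitivity efficacy analysis (including primary) related to panic attack events as specified". The other FAS, restricted to the second eDiary version, is for "All efficacy analysis (including primary) related to panic attack events captured by eDiary". The same table defines ITT as everyone randomised and the Safety Analysis Set as everyone randomised who took at least one dose. SAP 5.17 puts all safety analyses on the Safety Analysis Set.

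Protocol Table 7 has a FAS for non-panic-attack endpoints with the same definition as FAS: Expanded, and gives its use as "All other efficacy analysis". SAP Table 14 has no row with that use.

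**The concern.** A summary of important deviations is where a reader looks, by arm, for eligibility errors at randomisation. Here its denominator is a set from which those participants have already been removed because of that error, so the summary cannot show it, however many cases there are.

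The exposure table has a related problem. A participant who was dosed but ineligible, or dosed without a valid diary baseline, counts in the adverse-event tables but not in the table of who received IMP and for how long. The exposure denominator behind the safety results may then not match the safety denominator. Treatment discontinuations would also be tabulated twice, on all randomised participants in SAP 5.6 and on FAS: Expanded in SAP 5.8, and the two counts could differ.

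The smaller matter is that PDSS (the first key secondary endpoint), CGI-S, HAM-A, SDS and EQ-5D-5L have no analysis set named in the SAP. For PDSS, SAP 5.12.1.1 and 5.13 give only the estimand's target population, which does not tell a programmer which records to use.

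**Working it through.** **1. Who is missing from the two summaries.** Let R be the number randomised and U the number randomised but never dosed. Among the dosed, let E be those randomised in error without meeting eligibility, and V the remaining participants with no valid baseline panic-attack assessment. From the definitions in SAP Table 14:

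- ITT = R
- Safety Analysis Set = R − U
- FAS: Expanded = R − U − E − V

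The deviation summary (5.20) is therefore short of ITT by U + E + V. The exposure summary (5.8) is short of the Safety Analysis Set by E + V. All of E is absent from both summaries by definition. Neither document gives U, E or V, and each could be zero, so no size can be put on this part.

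**2. Where the omitted participants still appear.**

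| Item | Set | SAP section |
|---|---|---|
| Summary of important deviations | FAS: Expanded | 5.20 |
| Listing of all deviations | All randomised | 5.20, with 9.4 |
| Number in each set; set membership per participant | Summary and listing | 5.6 |
| Discontinuations with reasons; days on study | All randomised | 5.6 |
| Days on IMP; compliance | FAS: Expanded only | 5.8 |
| Adverse events | Safety Analysis Set | 5.17 |

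Two things have no summary on a wider set: important deviations by category, and days on IMP with compliance.

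**3. The non-diary endpoints.** The plan's own total reproduces: 2 × 114 + 18 = 246 randomised, of whom 18 used the earlier eDiary (SAP 1.2; protocol 9.5). At the planned size:

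- FAS: Expanded keeps up to 246 participants.
- The diary-restricted FAS keeps up to 246 − 18 = 228.
- Share lost: 18/246 = 7.3%.
- Standard error factor: √(246/228) = 1.039, an increase of 3.9%.
- Detectable standardised difference at 80% power, two-sided 0.05, calculated as (1.960 + 0.842) × √(4/N): 0.357 at N = 246 and 0.371 at N = 228.

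The figure of 18 is an upper bound, because some of those participants could fail another FAS criterion. SAP section 6 says the planned size will not be reached but gives no number. Over an assumed range of numbers randomised:

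| Randomised (assumed) | 18 as a share | Increase in SE, √(N/(N − 18)) − 1 |
|---|---|---|
| 200 | 9% | 4.8% |
| 150 | 12% | 6.6% |
| 100 | 18% | 10.4% |
| 60 | 30% | 19.5% |

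These figures apply only if the diary-restricted set were used for the non-diary endpoints.

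**The case against.** A reader might infer that eligibility errors would vanish from the study report. They would not. All deviations are listed, SAP 9.4 prepares listings for all randomised participants, and SAP 5.6 shows the count in each set and each participant's membership. Discontinuation reasons are also tabulated on everyone randomised. This much stands. What remains is that a listing does not replace a by-arm summary, and SAP 5.6 supplies neither days on IMP nor compliance.

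It can also be said that the protocol names no set for deviations or exposure, so the SAP contradicts nothing. That is correct: this is a weakness in the SAP's own choice of set, not a conflict between the documents.

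The more tempting inference is that the SAP drops the 18 earlier-diary participants from PDSS. The documents do not support it:

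- The diary-restricted FAS is limited by its own row to panic attack events captured by eDiary, and PDSS is clinician-administered.
- Protocol Table 7, and the version 3.0 rationale for the sample-size change, keep these participants for efficacy analyses that do not use the eDiary.
- SAP section 6 lists no change on this point.
- SAP 5.13 gives both diary endpoints a sensitivity analysis across eDiary versions and gives PDSS none, which fits PDSS never having been restricted by version.

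Against that, SAP 1 says its planned analyses supersede the protocol's, and SAP 5.9 describes the efficacy variables generally as diary-based, which is not true of PDSS. The gap is a possible ambiguity, not an exclusion.

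**Conclusion.** The main point holds on the wording alone. FAS: Expanded is the wrong base for a deviation summary, because it removes those randomised in error before their eligibility errors can be counted. It is also the wrong base for exposure, because it can be smaller than the set used for adverse events. The number affected is unknown and may be zero, and the listings and the disposition table mitigate the effect. This is a reporting fault that does not alter any efficacy estimate.

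The Table 14 gap is secondary. The most that could be lost is 18 participants, or 7.3% of the planned 246 with about 3.9% on the standard error. The larger percentages depend on an assumed actual sample size, and every one of these figures depends on a reading that the documents do not favour. SAP section 6 already treats efficacy as exploratory and underpowered. The planned sample size itself is not in question.

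**What to change.** - SAP 5.20: summarise important deviations on the ITT set.
- SAP 5.8: summarise exposure, discontinuation and compliance on the Safety Analysis Set.
- SAP Table 14, FAS: Expanded row: add all non-eDiary efficacy endpoints (PDSS, CGI-S, HAM-A, SDS, EQ-5D-5L) to the use column and leave the definition as it is. It already matches protocol Table 7, including the requirement for a valid panic-attack baseline. Substituting each endpoint's own baseline would create a new set and is not needed here.

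The cost is three wording changes and the matching population flags in the table shells. Both replacement sets are already defined, and no new data are needed. If the SAP is closed, section 6 already provides for documenting departures in the clinical study report, and the changes can be recorded there.

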6. CHANGES IN THE PLANNED ANALYSES

Analysis methods described here reflect revisions to strategic focus and scope and will supersede those described in the protocol. In addition to changes corresponding to protocol amendments, the analysis plan differs from the statistical analysis section of the protocol as described below:

- As a result of early closure of enrollment and early treatment discontinuation of ongoing participants, planned sample size will not be achieved and proportion of participants with treatment discontinuation will be increased. The resulting sample size will have insufficient power for hypothesis tests and thus, efficacy analysis will be exploratory.
 - The following changes were made to the protocol-specified statistical analysis to reflect the strategic shift to an exploratory evaluation of efficacy
 - Multiplicity adjustments were removed
 - Most sensitivity analyses were removed
 - Supportive analyses involving panic attack-related endpoints were added using an expanded FAS population including all participants regardless of eDiary version used
- Description of handling of ICEs was expanded and revised for the primary and key secondary endpoints:
 - Additional detail was provided for different types of ICEs (eg, administration of rescue medication and treatment discontinuation)
 - Composite strategy was replaced with treatment policy and while on treatment strategies for handling ICEs for analysis of primary and key secondary endpoints
- Added description of missing diary data handling:
 - For the primary efficacy outcome (proportion of participants free of panic attacks), outcome for participants who did not report a panic attack and had <12/14 days of completed eDiary was set to missing, unless otherwise indicated
 - For key secondary efficacy outcome (change from baseline in the frequency of panic attacks), outcome for participants with <7/14 days of completed eDiary was set to missing
- The SAP replaced the SAS® procedure GLIMMIX (specified in protocol) with GENMOD to fit binomial repeated measures model to estimate the proportion of participants that were free of panic attack and the treatment difference. Although both procedures can fit binomial repeated measures model, model-fitting is more efficient with the GENMOD procedure.

Should any deviations from the analyses pre-specified in the authorized statistical analysis plan arise, such deviations will be documented in the final clinical study report.

7. REVISION HISTORY

Only one version of the Statistical Analysis Plan was finalized. There were no subsequent amendments to the original version.

9. APPENDICES

9.1. Schedule of Assessments

Trial Periods/Phases	Screening (2 weeks) ^a		Treatment									Follow-up (4 weeks)		
			Titration (2 weeks)			Maintenance (12 weeks)								
Visit/Contact	Screening/ Visit 1	Baseline/ Visit 2		Telephone Contact	Visit 3	Telephone Contact	Visit 4	Telephone Contact	Visit 5	Telephone Contact	Visit 6	Visit 7 (Telephone)	Visit 8 (Telephone)	Visit 9
Day	-16 to -2	-1	1	7	14	28	42	56	70	84	98/ET ^b	101	105	131
Window				±3 days								±1 day	±3 days	
Entrance and History														
Informed consent	X													
Review inclusion/exclusion criteria	X	X ^{c,d}												
Medical and psychiatric history ^e	←-----→													
MINI	X													
Demography	X													
History of drug and alcohol use	X													
Nicotine use and history	X	X			X		X		X		X			
Review of birth control methods	X	X			X		X		X		X			X
Breathalyzer test for alcohol ^f	X	X												
Dispense diary and train on use	X													
Efficacy Assessments														
Review diary including compliance with use of diary		X		X	X	X	X	X	X	X	X	X	X ^g	
PDSS	X	X					X		X		X			

Trial Periods/Phases	Screening (2 weeks) ^a		Treatment									Follow-up (4 weeks)		
			Titration (2 weeks)			Maintenance (12 weeks)								
Visit/Contact	Screening/ Visit 1	Baseline/ Visit 2		Telephone Contact	Visit 3	Telephone Contact	Visit 4	Telephone Contact	Visit 5	Telephone Contact	Visit 6	Visit 7 (Telephone)	Visit 8 (Telephone)	Visit 9
Day	-16 to -2	-1	1	7	14	28	42	56	70	84	98/ET ^b	101	105	131
Window				±3 days								±1 day	±3 days	
CGI-S		X			X		X		X		X			
Other Assessments														
SDS		X					X				X			
HAM-A		X			X		X		X		X			
EQ-5D-5L		X									X			
Safety Assessments														
Height (Screening only) and weight	X	X					X				X			
Physical/neurological examination ^h	X	X									X			
ECG ⁱ	X	X					X				X			
Vital signs ^j	X	X			X		X		X		X			
C-SSRS	X	X			X		X		X		X			
PWC											X ^k	X	X	
Prior/concomitant treatments ^l	←-----→													
Adverse event monitoring ^m			←-----→											
Laboratory														
Blood for safety laboratory	X	X			X		X		X		X			X
Serum pregnancy test ⁿ	X													
Urine pregnancy test ⁿ		X			X		X		X		X			X

Trial Periods/Phases	Screening (2 weeks) ^a		Treatment									Follow-up (4 weeks)		
			Titration (2 weeks)			Maintenance (12 weeks)								
Visit/Contact	Screening/ Visit 1	Baseline/ Visit 2		Telephone Contact	Visit 3	Telephone Contact	Visit 4	Telephone Contact	Visit 5	Telephone Contact	Visit 6	Visit 7 (Telephone)	Visit 8 (Telephone)	Visit 9
Day	-16 to -2	-1	1	7	14	28	42	56	70	84	98/ET ^b	101	105	131
Window				±3 days								±1 day	±3 days	
Urine for safety laboratory	X	X									X			
Urine drug screening ^o	X	X			X		X		X		X			
Screening only laboratory tests: hepatitis B, C, HIV, and serum FSH ^{p,q}	X													
PK blood sample ^r					X		X		X		X			
Blood sample for future biospecimen research ^s		X												
Other														
IMP dispensing		X ^t			X		X		X					
Dosing starts			X											

Abbreviations: BID=twice daily; CGI-S=Clinical Global Impression-Severity of Symptoms Scale; C-SSRS=Columbia-Suicide Severity Rating Scale; ECG=electrocardiogram; EQ-5D-5L=European Quality of Life; ET=early termination; FSH=follicle-stimulating hormone; HAM-A=Hamilton Anxiety Scale; HIV=human immunodeficiency virus; IMP=investigational medicinal product; MINI=Mini International Neuropsychiatric Interview; PCR=polymerase chain reaction; PDSS=Panic Disorder Severity Scale; PK=pharmacokinetic; PWC=Physician's Withdrawal Checklist; SDS=Sheehan Disability Scale.

^a Participants will enter a Screening Period of approximately 2 weeks (minimum 14 days). The Screening Period may be extended up to 28 days if needed following consultation with the medical monitor.

^b If a participant discontinues early, the participant should follow the safety follow-up procedures (Visits 7-9).

^c Review of inclusion/exclusion criteria includes review of diary data to assess panic attack frequency.

^d Inclusion/exclusion criteria will be assessed at Baseline to ensure ongoing participant eligibility, with the exception of age or assessments that are only scheduled during Screening (eg, height for body mass index calculation).

^e Medical occurrences that begin before the start of dosing with IMP but after obtaining informed consent should be collected as medical and/or psychiatric history.

^f A breathalyzer alcohol test is required at the Screening Visit and at Baseline. The alcohol test (breathalyzer or blood/urine) can be conducted at any time during the trial at the discretion of the investigator.

- ^g The diary will be collected through Visit 8 (Day 105). Physical devices will be collected at the last in-person visit.
- ^h Full physical and neurological examinations should be completed at Screening. Limited examinations (cardiovascular, pulmonary, and gastrointestinal) should be completed at all other specified time points. Symptom-driven physical and/or neurological examinations may be done at any time during the trial at the investigator's discretion.
- ⁱ 12-lead ECG assessments will be performed after the participant has been at rest for approximately 3 minutes. At Screening, the average of 3 consecutive ECGs collected 1 to 2 minutes apart will be used to determine participant eligibility; at Baseline, only 1 reading is required for determination of eligibility. Single ECGs will be obtained at all other time points. Additional ECGs can be performed at the investigator's discretion (eg, if abnormalities are noted).
- ^j Blood pressure and heart rate assessments should be performed in order to confirm eligibility (see Exclusion Criterion in Protocol Section 5.2). Triplicate supine heart rate and blood pressure measurements should be taken at approximately 1-minute intervals at the Screening Visit. Duplicate supine heart rate and blood pressure measurements will be taken at all other time points. The supine heart rate and blood pressure measurements will be followed by a single measurement after approximately 2 minutes in a standing position to allow for orthostatic assessments. Additional time points can be added at the investigator's discretion (eg, if abnormalities are noted). Further details are provided in Protocol Section 8.2.3 and in the Operations Manual.
- ^k Visit 6 will be considered the baseline assessment for the PWC.
- ^l Prior and concomitant medications, including cannabis products, should be recorded from Screening through the participant's last visit/contact.
- ^m Adverse events (serious and nonserious) should be recorded from the first dose of IMP on Day 1 (eg, the day after Baseline) through the participant's last visit/contact.
- ⁿ For women of childbearing potential only. Pregnancy tests can be performed at any time during the trial at the discretion of the investigator if pregnancy is suspected. Any urine pregnancy tests that are positive must be confirmed using a serum test.
- ^o Additional urine drug screening can be conducted at any time during the trial at the discretion of the investigator.
- ^p Reflex viral hepatitis C PCR testing if hepatitis C antibody is positive or indeterminate.
- ^q A confirmatory FSH is required for all postmenopausal women.
- ^r With participants maintaining their normal BID dosing routine, a single daytime blood sample for determination of plasma darigabat concentration will be collected at Visits 3, 4, 5, and 6. The date and time of the PK sample, as well as the time of ingestion of previous dose of IMP, will be recorded in the source documentation.
- ^s Future biospecimen research sample is optional and is only to be collected if signed consent is obtained from the participant. Sample can be collected at any time following confirmation of participant eligibility and prior to initiation of first dose.
- ^t Randomization will occur at Baseline and IMP will be dispensed after randomization. Participants will start taking IMP on Day 1 (eg, the day following their Baseline Visit). Dosing will continue through Visit 6 (Day 98) or ET.

